1.8 List of abbreviations	
AE	Adverse Event
AR	Adverse Reaction
CA	Competent Authority
CI	Chief Investigator
CRF	Case Report Form
CRO	Contract Research Organisation
СТА	Clinical Trial Authorisation
DMC	Data Monitoring Committee
GCP	Good Clinical Practice
NHS R&D	National Health Service Research & Development
PI	Principal Investigator
PIS	Participant Information Sheet
REC	Research Ethics Committee
SAE	Serious Adverse Event
SAR	Serious Adverse Reaction
SDV	Source Data Verification
SOP	Standard Operating Procedure
SUSAR	Suspected Unexpected Serious Adverse Reaction
TMF	Trial Master File

Trial Steering Committee

2. TRIAL FLOW CHART

Part A

3. BACKGROUND AND RATIONALE

3.1 Nephro-oncology: Treating people with kidney disease and cancer

Kidney disease is a major global health problem with over 850,000 deaths each year¹. In the United States alone, the prevalence of the condition ranges between 14 and 17% of the population (dependent on ethnicity group), with a significant morbidity and mortality burden. Advances in cancer therapeutics have resulted in increased life-expectancy for many cancer patients. Nephro-oncology is an emerging sub-speciality tasked with managing the complex group of patients affected by both kidney disease and cancer. Izzedine and Perazella (2015) described a 'bidirectional relationship' between cancer and chronic kidney disease (CKD)². They state 'cancer is an important complication noted in kidney disease as well as a major cause of morbidity and mortality in this group. On the other hand, improved cancer treatment has prolonged survival, but also increased the development of acute and chronic kidney disease.' Patients with cancer who are receiving anti-cancer treatment are at risk of acute kidney injury (AKI) for many reasons including direct nephrotoxicity, severe dehydration, intrinsic paraneoplastic renal diseases and increased susceptibility to infection and sepsis owing to their immunosuppressed state. Abudayyeh et al (2014) described 'onconephrology' and found that this group of patients are 'increasingly complex to manage because of the wider use of conditioning regimens and SCT (stem cell transplantation) and the introduction of newer and potentially nephrotoxic cancer therapies'3.

3.2 Access to clinical trials and current barriers

Murthy et al (2004) found that recruitment in cancer clinical trials was low for all patient groups⁴. Specifically, they found that racial minorities, women and the elderly were less likely to be recruited in to cancer clinical trials than white people, men and younger patients. They also found that the proportion of black people who have been recruited to trials had reduced in 'recent years'. Ford et al (2007) carried out a systematic review of possible barriers to recruitment in to clinical trials and found they were numerous. Reasons included awareness and education with regards to clinical trials and opportunity to enrol (including co-morbidity exclusion)⁵.

Current evidence suggests that people with reduced kidney function may have an increased risk of getting cancer⁶ and that when cancer does occur their outcomes may be worse⁷. These patients may not be eligible for standard treatment options due to their reduced kidney function. However, at the current time, they are also not eligible for most oncology trials. This is because trial entry for majority of clinical trials is restricted to people with an eGFR (glomerular filtration rate) of above a certain standard level (for example ≥50ml/min). This is a largely arbitrary threshold and many drugs trialled are only partially renally excreted, if at all, therefore the clinical reasoning behind the cut off is

fundamentally flawed. Furthermore, yes/no to trial access is decided on a single time-point test at selection. This means that someone with a variable/uncontrolled renal function who happened to be eGFR 51ml/min on that day could access a trial, but someone with a more stable, managed renal function of eGFR 49ml/min would not. When in fact, the person with managed function may well cope better with the experimental drug.

Due to perceived risks of renal toxicity and causing harm to patients with CKD, patients with reduced kidney function are often excluded from cancer clinical trials⁸. Increasingly, the participation and barriers to recruiting in to cancer clinical trials is concerning, as is their lack of a true reflection of the 'real world' cancer population.

Jin et al (2017) performed a comprehensive review of the eligibility criteria for cancer clinical trials and stated, 'our findings suggest that eligibility criteria for current clinical trials tend to narrowly define the study population and limit the study to lower-risk patients, which may not be reflective of the greater patient population outside of the study'9. This has also been described in other studies which argue the tight inclusion/exclusion criterion of clinical trials lead to lower patient recruitment, increased timescales and cost and reduced relatability of trials to the general population¹⁰. Lichtman et al (2017) published recommendations to work towards modernising clinical trial eligibility criteria¹¹. They found that 'exclusion of patients with a CrCl < 60ml/min would preclude between 20.3% and 45.9% of patients from participating in clinical trials' and suggested that this was likely a conservative estimate. They recommended that the inclusion criteria for cancer clinical trials, with regards to renal impairment, should be relaxed in certain situations including where the available clinical and non-clinical data indicates that it is safe for use in people with renal impairment; also, if renal clearance and nephrotoxicity is not of concern then a cut off of CrCl > 30mls/min (rather than commonly used >60mls/min) should be utilised.

3.3 Renal monitoring in oncology trials

Patients receiving anti-cancer therapies are at risk of renal insults for a multitude of reasons, including the treatments themselves, the underlying disease process and their possible higher risk of infections/sepsis and dehydration¹². Increasing the monitoring of these patients could possibly lead to earlier identification of renal problems, allowing for greater medical support and potentially continuation on anti-cancer treatments that might have otherwise been stopped. Currently, when a patient is receiving chemotherapy, their kidney function is monitored at scheduled hospital appointments which may miss changes in creatinine indicating possible kidney damage, compounded by the fact that acute kidney injury is commonly associated with non-specific symptoms which could be attributed to chemotherapy side effects or the effects of cancer itself. Repeated episodes of AKI may lead to an increased risk of chronic kidney disease¹³. If these episodes of kidney injury can be picked up earlier, it may lead to reduced progression to more significant kidney dysfunction.

3.4 Prompt detection and diagnosis of AKI may improve the outcomes of AKI

AKI is described by the 'Think Kidneys Awareness Campaign' as a 'sudden and recent' decline in kidney function¹⁴. Prompt intervention focusing on the basic elements of care can improve the outcomes of AKI¹⁵. However, AKI is often poorly recognised by patients and clinicians¹⁶. To ensure that AKI cases are detected and diagnosed in a timely, consistent manner, the NHS recommends use of a standardised algorithm based on changes in serum creatinine levels¹⁷. The algorithm is intended for use as part of a Laboratory Information Management System (LIMS), to identify and classify potential cases of AKI from laboratory data in real time. Application of the algorithm is currently limited to hospital settings, but it is anticipated that the algorithm will also be used in primary care, subject to appropriate preparation¹⁶.

Several papers have been published studying the effect of e-alerts on the mortality and AKI progression in patients with AKI, albeit all in the hospital setting. Colpaert et al (2012) enrolled 951 patients into a prospective interventional study evaluating whether an electronic alert system would influence therapeutic interventions in AKI cases and progression of AKI. They found that a higher percentage of patients within the alert group had therapeutic intervention commenced within 60 minutes of the alert. They also found a 'borderline significant' improvement in outcomes of AKI, in the short term, in the alert group¹⁸. However, Wilson et al (2015) found that an e-alert system did not improve clinical outcomes in patients with AKI¹⁹. In this randomised controlled trial, 2393 participants were enrolled and randomised to the standard care group and e-alert group. Maximum change in creatinine, dialysis and death at 7 days did not differ between the 2 groups. Clearly this area of AKI management needs further investigation, especially in the oncology setting.

Patients receiving anti-cancer treatments are at higher risk of AKI. Salahudeen et al (2013) found that rates of AKI in patients admitted to a cancer centre were higher than that in a non-cancer centre²⁰. Lam et al (2012) discuss the different cause of AKI in the cancer patient¹². These causes include pre-renal causes – nausea, vomiting and diarrhoea, concomitant medications such as NSAIDS, ACE inhibitors and diuretics, hypercalcaemia; intrinsic causes – lymphomatous infiltration of the kidney, cast nephropathy, tumour lysis syndrome; and post renal causes – obstruction of the urinary tract.

3.5 Self-monitoring of kidney function could help manage risks associated with cancer treatments

Usually, renal function is monitored at set times during a clinical trial, unless an unexpected event warrants it being checked. If monitoring of renal function can be improved upon, this could potentially lead to earlier detection of adverse renal events and a subsequent improvement in patient outcomes.

Self-monitoring has been shown to be an effective and acceptable form of monitoring in other chronic health conditions such as diabetes and anti-coagulation monitoring. Gardiner et al (2004) explored self-testing of INR in the home compared to in hospital laboratory testing in 84 patients. They found that 87% of patients found self-testing straight forward and were confident in the result and that 77% preferred self-testing²¹. Karter et al (2001) found that 'more frequent self-monitoring of blood glucose levels was associated with clinically and statistically better glycaemic control regardless of diabetes type or therapy¹²². Self-monitoring of kidney function has been described in the literature previously. Van der Boog et al (2015) explored self-monitoring of renal function in the kidney transplant population²³. They found that this population of patients were highly motivated to self-monitor and reported high levels of satisfaction with self-monitoring. If self-monitoring of renal function in cancer clinical trials can be shown to be acceptable and effective it could ultimately lead to the inclusion of patients with reduced kidney function being recruited to cancer clinical trials in a safe and accepted manner.

3.6 Renal Biomarkers

Renal biomarkers are an increasingly researched area. Limitations of the traditional marker of kidney function – creatinine – are well established²⁴. Research in to renal biomarkers in the cancer population is a less studied area. It is hoped that this study will add to the body of knowledge by collecting samples of urine and whole blood to analyse for cystatin C and other renal biomarkers. Assessing renal biomarkers and their role in the cancer population could also add to the monitoring of kidney function and potentially pick up signals of deterioration earlier and allow patients with reduced kidney function to be enrolled in to clinical trials.

3.7 How this study addresses the research question

Part A of this study aims to explore whether patients who are currently receiving anti-cancer treatments are willing and able to perform intensive home monitoring of creatinine and send their results in to a cloud environment via an app to be run through an amended version of the NICE AKI algorithm to assess for evidence of AKI¹⁷. The algorithm has been amended for practicality and feasibility reasons. It is hoped that this will show the process to be convenient and acceptable to patients and clinicians and that the results are reliable. Furthermore, Part B of the study aims to show that home monitoring of creatinine will detect adverse kidney events and AKI earlier as compared to standard of care monitoring along with less overall change in kidney function in the intensively monitored group as compared with the standard of care group.

It is increasingly apparent that treatment options for this complex group of patients affected by both cancer and CKD are needed. Expanding the population of people with reduced kidney function recruited into clinical trials will be one way of meeting this clinical need.

3.8 Impact of this study on existing research

It is hoped that this research will show that home monitoring of renal function in a cancer population is not only acceptable to patients and clinicians but also leads to clinical benefit in terms of time to diagnosis of adverse renal events and acute kidney injury. This in turn may pave the way for patients with reduced renal function to be recruited in to cancer clinical trials in the future. This will ensure that future research has broader applicability as well as providing much needed information on how best to approach the treatment of a challenging group of patients who have both kidney disease and cancer.

3.9 Patient and public involvement

There were 17 individual interactions with people currently involved in early oncology trials within The Christie NHS Foundation Trust. These included patients, carers, and staff, and focussed mainly on gaining insight into the applicability of the research question, usability and practicality of the device, performing readings, and the information provided. Feedback gathered during these discussions has directly informed the protocol and processes described within.

Two focus groups have also been conducted. The first with 3 participants who have previously had cancer. The second, with 4 renal patients at various stages of their treatment journey, 2 of whom had also received a treatment for cancer that affected their kidney function. The project was unanimously felt to be worthwhile and many were surprised by the current limitations that reduced kidney function can have on peoples' cancer-treatment options. Both groups liked the idea of having some control over their results and having more responsibility over their own health. Participants from the renal focus group specifically embraced taking their own readings and thought that it would be motivating for taking ownership of their health overall. Both groups of participants questioned whether a study involving this sort of technology and smart phones/apps would exclude a section of the population who are not 'tech-literate' or able to perform the reading for various reasons such as dexterity problems. They queried whether a reading could be carried out by carers as, at certain timepoints, patients undergoing cancer treatments may be intensely fatigued or unable to carry out readings for other reasons. If a patient would like to participate in the study and has a carer they would like to perform the testing, they will be trained to take the readings as such. In addition to providing feedback on the practicality of the approach and information provided, they have since reviewed and approved the final information leaflets and videos accompanying this trial.

4. STUDY AIMS AND OBJECTIVES

This study will be delivered in two sections: Part A and Part B. The aim of Part A is to assess whether intensive home monitoring of creatinine is an acceptable and feasible form of monitoring for patients. Part B of the study will aim to show earlier detection of deteriorating kidney function and AKI as compared to standard of care renal monitoring.

Table 2: Study objectives, outcomes and measures

Objectives	Outcome Measures	Timepoint(s) of evaluation of this outcome measure (if applicable)
Primary Objectives		
Part A: To evaluate patient acceptance of intensive home-monitoring of whole-blood creatinine.	Questionnaire and interview Absolute number of creatinine readings received-expected vs actual Time sample taken vs. time expected to take Value sent/received vs. value on device (when downloaded at the end of the study period)	Week 4
Part B: To evaluate the potential for earlier diagnosis of AKI/change in renal function with intensive home-monitoring of whole-blood creatinine.	Time from beginning of current cycle treatment to detection of AKI by amended algorithm or clinician/laboratory reading Severity of AKI at detection (as	Throughout study period
	per Kidney Disease Improving Global Outcomes AKI Work Group staging) Overall change in renal function from beginning to end of study period	

Secondary Objectives		
Part B: To assess whether intensive monitoring influences the change in kidney function over the study period compared to standard of care	Comparing kidney function at the beginning and end of the study	Weeks 1 and 6
Part B: To assess whether home monitoring of kidney function has a positive impact on a patient's quality of life.	Medical outcomes study short form 36 (SF-36) questionnaire	Week 6
Part B: To evaluate the adherence of patients to intensive home monitoring regimen	Absolute number of creatinine readings received Time sample taken vs. time expected to take Value sent/received vs. value on device (when downloaded at the end of the study period)	Week 6
Exploratory Objectives		
Part A: Using data gathered to improve and test amended AKI algorithm	Amended algorithm outcome vs clinician assessment Feedback and analysis from interviews and questionnaires	On completion of Part A
Part B: To explore the value of novel renal biomarkers in the cancer population for early detection and monitoring of AKI.	Urine and serum analysis	Throughout study period

Part B: Document any other issues that patients may have experienced during the study period.	Patient interview	Week 6
Part B: Clinician opinions towards home monitoring and the impact it could have on their treatment schedules for patients.	Clinician interview	Week 6
Part B: Are there ethical/justice considerations in carrying out studies which require access to smart phones/socioeconomic factors	Analysis of demographic information of patients enrolled, and those who declined, in study and those who decline to take part Patient interview	Week 6

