5.2 Part B

If, following Part A, the process is found to be an acceptable form of monitoring to patients, the study will continue to Part B. This will evaluate the potential for earlier diagnosis of AKI with intensive home monitoring of kidney function (plus standard of care monitoring) compared with standard of care only. The decision of whether to proceed to this stage of the study is described in further detail below. Participants who have been recruited to Part A of the study can continue to Part B if they so wish (and will be randomised).

Part B will enrol 60 patients being treated for cancer with potentially nephrotoxic anti-cancer therapies, randomised to either the intensive monitoring (device) group or the standard of care monitoring group, in a 1:1 ratio. Participants in both groups will be asked to complete a quality of life questionnaire at baseline. Both groups will receive standard of care monitoring of kidney function. In addition, participants in the intensive monitoring group will upload their creatinine reading three times per week (Mon/Wed/Fri) for 6 weeks. As in Part A, participants in the intensive monitoring group will be required to access the app on their own compatible device and upload their readings over their own internet connection. In both study arms, in line with scheduled clinic appointments (weeks B1, B3 and B6), blood and urine will be collected for exploratory biomarker analysis, along with renal function and cystatin C. When a participant attends a clinic appointment, a creatinine reading will be taken (either by the study participant or by a member of the study team) using the device, for comparison with the laboratory reading of creatinine taken that day.

During Part B of the study, when a participant has submitted their creatinine reading they will receive a successful submission message on the app and may receive feedback based on their reading (this depends on feedback from Part A of the study, performance of the amended algorithm from Part A and development of the smart phone application). As with Part A, participants will be directed to their

parent medical team if there is concern over their reading. Creatinine readings and AKI alerts from the algorithm will also be reviewed by the Chief Investigator once a week and highlighted to the parent medical team if there are concerns.

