9. STATISTICAL CONSIDERATIONS AND DATA ANALYSIS

For Part A of the study, a powered sample size calculation has not taken place. In line with published recommendations³¹ 12 patients will be recruited to receive the StatSensor® to assess the general process of taking creatinine readings and sending in results via the app. Descriptive statistics will be used to summarise demographic data and clinical variables. Categorical data will be reported using frequencies and percentages. Quantitative variables will be reported using either the mean and standard deviation or the median and interquartile range depending on the distribution of the data. The standard error of the mean will also be calculated.

For Part B current powered sample size calculations estimate 30 study participants to be satisfactory. This number will be sufficient as overall creatinine levels will be used as an end point for higher statistical power as well as AKI rate. A Student's t-test and one-way ANOVA test will be used to analyse data for statistical significance.

The significance has been calculated using the assumption during standard treatment for head and neck cancer, the mean creatinine readings are 1.2 +/- 0.2 mg/dl, with closer monitoring having the potential to bring it down to 0.9+/-0.2 mg/dl based on the results of docetaxel, cisplatin, and 5-fluorouracil therapy³².

Themes from the interviews will be developed and analysed in more detail in line with published guidance on qualitative study analysis³³.

Analysis of data from this study will be in conjunction with the statistics department of the sponsor and in-house statistician support and other statistical analyses will be used as appropriate.

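### The first Part B primary measure, time from cycle start to AKI detection, mixes AKI onset with detection delay, so a null or reversed difference could not be told apart from prevention of AKI

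*Protocol*

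**What the plan says.** Section 4 sets the direction of benefit: "Part B of the study will aim to show earlier detection of deteriorating kidney function and AKI as compared to standard of care renal monitoring". The first outcome measure in the Part B primary row of Table 2 is "Time from beginning of current cycle treatment to detection of AKI by amended algorithm or clinician/laboratory reading". Severity of AKI at detection and overall change in renal function stand in the same row.

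Other sections expect an effect on the kidney as well as on the time of diagnosis. Section 3.7 hopes that home monitoring "will detect adverse kidney events and AKI earlier as compared to standard of care monitoring along with less overall change in kidney function". Section 9 assumes that under standard treatment "the mean creatinine readings are 1.2 +/- 0.2 mg/dl, with closer monitoring having the potential to bring it down to 0.9+/-0.2 mg/dl", and says that "overall creatinine levels will be used as an end point for higher statistical power as well as AKI rate".

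On testing, section 5.2 states: "Both groups will receive standard of care monitoring of kidney function". The device arm adds readings on Monday, Wednesday and Friday for six weeks, and clinic blood is taken in both arms at weeks B1, B3 and B6. Section 9 names a t-test and one-way ANOVA. The protocol does not say how a participant without AKI enters the time measure.

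**The concern.** The clock starts at the treatment cycle, not at the kidney injury. The measured time is therefore onset time plus detection delay. Home monitoring can act on both parts, in opposite directions:

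- Faster detection shortens the delay and so shortens the measure.
- An AKI that is averted or postponed lengthens the measure, or leaves the participant without an event.

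If both happen, the difference between arms is a net of the two, and nothing in the measure separates them. A null or reversed result could mean that the device failed to bring diagnosis forward, or that it brought diagnosis forward and also prevented AKI. The primary question would be left unanswered. Naming a survival method would not cure this, because the mixture lies in the definition of the time and not in the test applied to it.

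**Working it through.** **The plan's own figure.** There is none for this measure. The sample size in section 9 rests on mean creatinine (difference 1.2 − 0.9 = 0.3 mg/dl, SD 0.2) and says nothing about time to detection. What follows is an illustration.

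**Inputs from the protocol.** Six weeks (42 days) of follow-up; device readings on Monday, Wednesday and Friday; clinic tests at B1, B3 and B6 (section 5.2).

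**Assumptions.** AKI risk in controls p = 30% (20% and 50% also run); onset uniform over 42 days; AKI detected at the next scheduled test, without error; visits on the exact day, although the protocol allows one week either way; standard-care tests at the spacings tabled below. A fraction f of AKI is prevented in the device arm. AKI-free participants count as 42 days.

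**Formula.** Let L be the mean days between detection and day 42 among AKI cases. Then

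restricted-mean difference (device − control) = p × [L_control − (1 − f) × L_device],

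which is zero at f = 1 − L_control / L_device. The risk p drops out of the break-even point.

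**Device arm.** The gaps between readings are 2, 2 and 3 days, so the mean wait is (4 + 4 + 9) / (2 × 7) = 1.2 days. Mean detection is at day 21 + 1.2 = 22.2, and L_device = 42 − 22.2 = 19.8.

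**Break-even by control testing.**

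| Control tests (days) | Mean detection | L_control | f at zero difference |
|---|---|---|---|
| 14, 42 (B3 and B6, with B1 as day 0) | 32.7 | 9.3 | 1 − 9.3/19.8 = 53% |
| 21, 42 | 31.5 | 10.5 | 1 − 10.5/19.8 = 47% |
| 14, 28, 42 | 28.0 | 14.0 | 1 − 14.0/19.8 = 29% |
| weekly | 24.5 | 17.5 | 1 − 17.5/19.8 = 12% |

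**Difference in days, control tests at days 21 and 42, p = 30%.** The gain per AKI is 31.5 − 22.2 = 9.3 days throughout.

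- f = 0: 0.30 × (10.5 − 19.8) = −2.8
- f = 25%: 0.30 × (10.5 − 14.85) = −1.3
- f = 50%: 0.30 × (10.5 − 9.9) = +0.2
- f = 75%: 0.30 × (10.5 − 4.95) = +1.7

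A simulation with 400,000 participants per arm gave −2.79, −1.32, +0.17 and +1.65. At control risks of 20% and 50% the sign changed between the same two values of f.

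**Other ways of reading the measure, same simulation.** The event-rate ratio (device/control; above 1 reads as earlier) was 1.08 with no prevention, 0.96 at 10% and 0.78 at 25%. It passes 1 at about 10% prevented or less, so at 25% it points the opposite way from the restricted mean. Among detected cases only, the means stayed at about 22.2 against 31.5 days at every level of prevention. That reading shows no opposition, but it compares groups selected after randomisation.

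**The case against.** The strongest reply is that the protocol never states prevention of a first AKI as an aim. Section 3.3 speaks of less progression once an injury is picked up, section 3.4 of better outcomes of AKI, and section 3.8 of time to diagnosis. Benefits that follow detection leave time to first detection unchanged. This stands: prevention is an inference from section 3.7 and from the creatinine assumption and AKI-rate end point in section 9. Weekly review by the Chief Investigator also makes a large preventive effect less likely.

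Second, the handling of AKI-free participants may be settled in an analysis plan that is not at hand. That is fair, but the origin of the clock is fixed in the protocol. Counting everyone leaves the mixture in place, and counting only detected cases gives up the randomised comparison.

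Third, severity at detection, renal-function change and AKI rate are already listed, so prevention could show there. This also stands, and it limits the point to one measure. None of those three measures how early AKI is diagnosed.

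A reader might go further and infer that section 9 leaves almost no AKI in the device arm. An assumed cut-off of 1.35 mg/dl (1.5 × 0.9) lies 0.75 SD above 1.2 and 2.25 SD above 0.9, which gives tail areas of 22.7% and 1.2%, or 6.8 against 0.4 of 30. The documents do not support calling these AKI cases. Section 9 gives no individual baseline and no AKI risk, and section 3.4 describes detection from changes in creatinine, not from one absolute level across patients.

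**Conclusion.** The point holds for this one measure. Time from cycle start to detection cannot by itself show whether diagnosis came earlier, because any averted or postponed AKI moves it the other way once AKI-free participants are counted. On restricted mean time the net effect reaches zero at about 47% prevented with three-weekly control tests, 29% with two-weekly and 12% with weekly tests. These figures rest on uniform onset, error-free detection at the next test and assumed control-test spacing; the break-even does not depend on the assumed AKI risk.

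Two stronger readings are tempting and should not be drawn. One is that the two effects simply cancel: they oppose each other, and a zero net difference needs particular magnitudes. The other is that a favourable result would require monitoring to prevent little AKI: with 25% prevented and three-weekly control tests the restricted mean still favours the device by 1.3 days.

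**What to change.** Keep the randomised time-to-detection comparison and make two additions to Table 2 and section 9.

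1. State that the comparison is interpreted only together with AKI incidence by arm, in all randomised participants, taken from laboratory creatinine on the schedule common to both arms.
2. Add, as a supportive descriptive measure of earlier diagnosis, the paired lead time in the device arm: days from the first algorithm alert to the first standard-of-care laboratory creatinine or clinician diagnosis that shows the AKI. Report separately the alerts that the next scheduled laboratory test does not confirm, or shows to have resolved. The pairing is possible because standard monitoring continues in this arm.

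The cost is one reworded row and a few sentences of analysis text. The home readings and clinic bloods are already planned, so no patients or samples are added.

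The paired measure has limits. It is not randomised, and it rests on few events: at the assumed 30% risk, 30 participants give 0.30 × 30 = 9 AKI before any prevention. Action taken on an alert can also resolve the AKI before the next standard test, or prompt the clinician diagnosis itself. Incidence from the common schedule counts AKI visible at those tests and can miss episodes between them.
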